#### *Research question:*

- 1. What is de the difference in the proportion of study patients seen by the GP between intervention and control weekends?
  - 1.1. Is this proportion associated with the patient's presentation (chosen eMTS flowchart and urgency)?
  - 1.2. Is this proportion associated with the occupancy rate of the ED and/or GPC?
  - 1.3. Is this proportion associated with the operating triage-nurses and/or the operating emergency physician?
  - 1.4. Is this proportion associated with the patient's background characteristics? (sex, age, community, insurance status)?
  - 1.5. Is there seasonal variation in this proportion?

Secondary hypothesis: a nurse using the eMTS is able to detect primary care patients. We can assess the correctness of the nurse's allocation advice as a diagnostic instrument.

The results of the triage consult is either a GPC or ED advice. Arbitrarily we will call a GPC advice a positive diagnosis. The gold standard is the opinion of the physician (either emergency physician or GP) after the consultation. This standard is used in almost all of the literature(3), as no better gold standard is available. We are aware of some disadvantages: this opinion depends on the personality and other characteristics of the treating physician and some patients have presentations suitable for both ED and GPC. On the other hand, agreement between nurse and physician is important for the feasibility of extended triage.

The way we will measure the correctness of the triage advice depends on whether the patient is compliant to this advice. This makes Table 1 more complex:

	Patient goes to GPC		Patient goes to ED	
Opinion physician	GPC correct	Had to go to ED	ED correct	Had to go to GPC
Advice GPC	Correct decision 1	False positive 1	False positive 2	Correct decision 2
Advice ED	False negative 1	Correct decision 3	Correct decision 4	False negative 2

Table 2: patient categories for the eMTS as a diagnostic instrument

Because our eMTS is risk adverse, we already know we will have a certain amount of false negative 2: patients who are compliant to the advice of ED although they had to go to the GPC according to the emergency physician. This category is not our primary focus.

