#### *Research questions:*

- 2. What is the validity of the eMTS as a preliminary diagnostic instrument to detect a primary care patient?
  - 2.1. What is the proportion of correct extended triage decisions measured by comparing the triage advice with the urcenty evaluation of the physician?
  - 2.2. What is the proportion of correct extended triage decisions with advice GP measured by the proportion of referrals within this category?
  - 2.3. What is the proportion of patients wrongly assigned to GPC (all false positives)?
  - 2.4. What is the proportion of patients wrongly assigned to GPC who did go to the GPC (type 1 false positives)
- 3. What is the proportion of patients who are not compliant to a correct GPC advice (Correct decision 2).
  - 3.1. What are the determinants for this non-compliance? (same determinants as studied in question 1.1-1.4)
- 4. What is the proportion of patients in which the nurse gives another advice comparing to the eMTS?
- 5. Does the intervention influence the number of patients left without being seen?
- 6. What is the shift in workload during the different phases of this study for all participating healthcare providers (GPs, triage nurses and ED physicians)?
- 7. Does the epidemiology in terms of reasons for encounter and diagnoses at both OOH services differ between intervention and control weekends?
- 8. What is the proportion of patients who return to the ED within two weeks for each of the categories described in table 2?

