# Methodology for the medical aspect

The data necessary for this work package are part of a routine clinical report. We will use three types of these reports: triage-consultation reports, ED consultation reports and GPC consultation reports. We will collect these data using the iCAREdata database. This database can link our three types of clinical reports using an irreversibly coded national number. Due to data protection rules, the iCAREdata data manager will execute all queries and only aggregated results will be transferred to the researchers. For more complex statistical analysis, the data manager will transfer an analysis specific table or the analysis will be carried out on the computer of the data manager in cooperation between the researcher and the data-manager. A detailed data management plan is available. The correctness of a triage decision depends on the patient's situation:

- At the GPC (patients compliant to a GPC advice or non-compliant to an ED advice): the ratio of patients referred to an ED to the total number of patients coming from the ED of AZ Monica.
- At the ED (patients compliant to an ED advice or non-compliant to a GPC advice): the physician will answer the same question for all patients: "Should this patient better go to the GPC?". The correctness is defined as the ratio of the patients with a positive answer to this question to the total number of patients staying at the ED after triage.

The parameters of interest in questions 1 through 8 are (conditional) proportions, which calls for analysis by a non-linear model (e.g. binary logistic regression). The study design results in the creation of nested data, where patients are nested in weekends, and weekends are nested in (multiple) nurses. Appropriate analysis of such auto-correlated data requires a nonlinear mixed model. During the first months, data will be used to produce point-estimates of these proportions (e.g., patients seen by GP, correct triage decisions, all false positives, type 1 false positives, patients left without being seen, etc.). With increasing duration of the study, incoming data will be used to explain variability of these probabilities in terms of patient background characteristics, operating nurses/emergency physician, season, etc. Statistical assistance will be called for in order to conduct these analyses.

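### Questions 3 and 3.1 restrict refusal to GPC advice judged correct after the patient's choice, by a rule that differs with that choice, so labelling and patient behaviour cannot be separated

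*Combined protocol and SAP*

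**What the plan says.** **The question.** In the list of research questions for the medical aspect, question 3 reads: "What is the proportion of patients who are not compliant to a correct GPC advice (Correct decision 2"). In Table 2 this cell holds patients advised to go to the GPC who went to the ED, and whom the emergency physician then judged suitable for the GPC. Question 3.1 asks for determinants, taken from questions 1.1 to 1.4. Question 1.3 includes the operating emergency physician.

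**When correctness is judged.** Under the secondary hypothesis: "The gold standard is the opinion of the physician (either emergency physician or GP) after the consultation". The same section adds: "The way we will measure the correctness of the triage advice depends on whether the patient is compliant to this advice".

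**How it is judged.** Methodology for the medical aspect gives two rules. At the GPC it uses "the ratio of patients referred to an ED to the total number of patients coming from the ED of AZ Monica". At the ED the physician answers "Should this patient better go to the GPC"?

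**Caveats given.** The secondary hypothesis concedes that "this opinion depends on the personality and other characteristics of the treating physician" and that "some patients have presentations suitable for both ED and GPC". These are raised for the gold standard in general and are not carried through to question 3 or 3.1.

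**Analysis.** A nonlinear mixed model is planned for questions 1 to 8. The plan has no common reference standard, no sensitivity analysis on the label, and no stated refusal measure whose denominator is fixed when the advice is given. Table 1 already contains the cells for such a measure.

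**The concern.** Question 3 selects patients on a label that does not exist when they decide. The label is produced afterwards, in one of two ways, depending on the decision under study. Referral by a GP is an action; the emergency physician's answer is an opinion. A patient who would be acceptable at either service, a group the protocol says exists, need not be referred by the GP and so counts as correctly advised after complying. The same patient, having refused, may draw a no from the emergency physician and drop out of question 3.

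The reported proportion can therefore move with the stringency of the label as well as with what patients do. In question 3.1, a factor that shifts the label on one side only can look like a determinant of refusal. One listed determinant, the operating emergency physician, is also the person who labels the refusers.

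At stake is the reading of a secondary question: how much inefficient refusal there is, and whom to target to reduce it.

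**Working it through.** The plan states no figure for question 3, so there is none to reproduce.

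**Inputs**

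- Denominator: not written. Assumed to be *Correct decision 1* (CD1) + *Correct decision 2* (CD2), the natural reading.
- c: refusal among GPC-advised patients who are seen. Not given; 25% assumed.
- a: share of compliers labelled correct, read as 1 minus the GPC referral share. Not given; 0.95 or 0.90 assumed.
- b: share of refusers labelled correct by the emergency physician. Not given; varied from 0.95 to 0.40.

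**Step 1: the identity.** Per GPC-advised patient seen, CD2 = c·b and CD1 = (1−c)·a. So

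- observed proportion = c·b / [c·b + (1−c)·a]
- observed odds = [c/(1−c)] × (b/a)

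**Step 2: numbers for c = 25%**

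| a | b | c·b | (1−c)·a | Observed |
|---|---|---|---|---|
| 0.95 | 0.95 | 0.2375 | 0.7125 | 25.0% |
| 0.95 | 0.90 | 0.2250 | 0.7125 | 24.0% |
| 0.95 | 0.80 | 0.2000 | 0.7125 | 21.9% |
| 0.95 | 0.60 | 0.1500 | 0.7125 | 17.4% |
| 0.95 | 0.40 | 0.1000 | 0.7125 | 12.3% |
| 0.90 | 0.95 | 0.2375 | 0.6750 | 26.0% |

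The result can lie below or above c. If the denominator were instead all GPC-advised patients seen, with CD2 still in the numerator, the result would be c·b (15% at b = 0.60), which also depends on the label.

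**Step 3: what the gap means.** Let s_R and s_C be the shares of refusers and compliers who would be suitable under one common rule. Then

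b/a = (s_R/s_C) × [(b/s_R) / (a/s_C)]

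The first factor is a true difference in suitability, which question 3 intends to capture. The second is the difference between the two rules. Take a = 0.95, b = 0.60, observed 17.4%:

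- If s_C = 0.95 and s_R = 0.60, the rules agree and 17.4% is the right answer to question 3.
- If s_C = s_R = 0.95, the right answer is 25.0%, and the whole gap comes from the ED rule being stricter.

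Both cases give the same observed data. No patient is judged under both rules, so the design cannot tell them apart.

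**Step 4: determinants (question 3.1).** Comparing two levels of a determinant, observed odds ratio = true odds ratio × ratio of the two b/a values.

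- *b/a equal at both levels.* With refusal of 40% and 25%, the true odds are 0.667 and 0.333, ratio 2.0. With b/a = 0.6 at both, they become 0.40 and 0.20, ratio still 2.0. No distortion.
- *b/a differs through the rater.* Two emergency physicians, both with c = 25% and a = 0.95. One labels 80% of refusers suitable, the other 40%. Odds are 0.2000/0.7125 = 0.281 and 0.1000/0.7125 = 0.140, ratio 2.0. The observed proportions are 21.9% and 12.3%, although refusal is the same.

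**Step 5: who is omitted.** GPC-advised patients who leave before a consultation (*Left without being seen type 1*) have no physician opinion and cannot enter CD1 or CD2. Question 3 also does not say that it is limited to intervention weekends, although Design of the clinical trial says control patients are not told their advice.

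**The case against.** The strongest reply is that question 3 does not ask for overall refusal. The text before the research questions says why this cell matters: these patients chose inefficiently, so there is room for improvement. If refusers really are less often suitable for the GPC, a figure below overall refusal is the correct answer. This stands. The gap between c and the observed proportion cannot be presented as error, and Step 3 shows why.

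Second, a characteristic that makes the ED more appropriate should also raise GP referral, so a and b may move together. This also stands. A reader might infer that anything inclining the emergency physician towards the ED will appear to predict compliance; that follows only if b/a changes across levels of the determinant. For ED occupancy, flowchart and urgency this is plausible, but for every determinant other than the emergency physician it is a risk and not a demonstrated effect.

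Third, the protocol discloses the choice-dependent measurement and rater variation, says no better gold standard is available, and lists the operating emergency physician among the determinants. This stands in part. Including the physician may adjust other coefficients for differences in strictness between physicians. It does not remove their average strictness from the proportion, and it leaves the physician's own coefficient mixing refusal with labelling.

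Fourth, questions 1.1 to 1.4 already examine determinants of being seen by the GP without the label. True, but the denominator there is all study patients, so they do not answer the question about refusing an advice.

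**Conclusion.** The point holds in limited form. Questions 3 and 3.1 condition on a label set after the choice by two rules that nothing in the plan makes equivalent. Under the assumed CD1 + CD2 denominator, the observed odds of refusal are those among all GPC-advised patients seen, multiplied by b/a. That factor blends true suitability with the difference between rules.

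A reader might infer that the rate and its determinants are shown to be biased, or that the protocol will understate refusal. The documents do not support either: they give no refusal rate, referral rate or ED agreement rate, so size and direction are open, and overstatement is possible (26.0% for 25% in the last row of the table). Nor is correctness defined by compliance. It is defined as the physician's opinion; only its measurement depends on compliance.

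For 3.1 the problem is direct for one determinant, the operating emergency physician. The false odds ratio of 2.0 rests on assumed values (80% against 40%, equal refusal, equal a) and on the two physicians differing in strictness and not in case mix.

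The primary question does not use the label and is unaffected.

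**What to change.** 1. Keep the *Correct decision 2* measure and write its denominator.
2. Alongside it, report refusal among all patients told a GPC advice on intervention weekends: Table 1 *Non-compliant patient GPC* over all *Advice GPC*, with *Left without being seen type 1* shown separately. This denominator is fixed before the choice and does not depend on a or b.
3. Fit the 3.1 determinant model to that outcome, at least for the operating emergency physician.
4. State in the plan that *Correct decision 2* results, including determinants, will be interpreted in light of the two labelling rules.

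**Cost.** Rewording of questions 3 and 3.1 and one further model. The Table 1 categories already follow from the planned data, and more patients enter the model. The downside is that refusal among all advised patients includes refusals that the emergency physician considers justified (*False positive 2*). It therefore supplements the question about room for improvement and does not replace it.

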# Scientific methodology of this project: is this service at this time the most appropriate for me?

[figure not shown]
Three aspects determine the most appropriate OOH service for a specific patient at a specific time:

- Medical aspects: is this service capable of handling the medical problem in an efficient and qualitative way? Is it safe?
- Financial aspects: is it the most cost effective service for both government and patient?
- *Process aspects:* can the delivered service satisfy the perceived needs of patients and staff? What are the major barriers and facilitators? What can we learn from reported incidents? How can we improve safety? This aspect is only briefly described in this protocol, as we will make a separate protocol.

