# Hypotheses and Research questions

#### Medical aspect

Our primary hypothesis: the extended triage intervention will lead to a substantial increase in the proportion of patients seen by the GP.

Without the intervention, all study patients can be divided in three categories: seen by ED, seen by GPC and left without being seen (after the triage). By adding the compliance of the patient to the allocation advice we get the following table:

	Patient goes to GPC	Patient goes to ED	Left without being seen
Advice GPC	Compliant patient GPC	Non-compliant patient GPC	Left without being seen type 1
Advice ED	Non-compliant patient ED	Compliant patient ED	Left without being seen type 2

Table 1: patient categories

The proportion of study patients seen at the GPC is a combination of patients compliant to a GPC advice and patients not compliant to an ED advice. The latter category will probably be small.

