We are mostly interested in false positive 1: patients who complied with the advice GPC but should have stayed at the ED. Some of these patients might be subject to a safety risk. For example, a patient with a heart attack allocated to the GPC might lose valuable time. This category is the same as the proportion of study patients allocated to the GP but referred back to the ED. We will give this category special attention in our process analysis.

Finally, we are also interested in the category correct decision 2: patients who are not compliant to a correct GPC advice. These patients made an inefficient decision so there is room for improvement.

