#### Design of the clinical trial

#### A controlled longitudinal prospective intervention trial

To answer the above-mentioned research questions we need a longitudinal prospective intervention trial.

To allow definitive conclusions for our questions we need a control group. Historical controls will have too much confounding (not all data is available, the ED was organised in a different way, the GPC was unknown for many patients). Individually randomised controls are impossible from a practical point of view and because of contamination (patients will talk to each other and will not understand why some get a GPC advice and others not). Finally, randomisation by shift is not possible because they overlap in time. Therefore, randomisation is only possible by weekend. We will roll out one control weekend out of every four intervention weekends.

During a control weekend, all data registration and collection will be the same as during intervention weekends but we will not inform patients about their allocation advice. The emergency physician will see all patients deciding to stay at the ED, without influence of the triage advice. As in standard clinical care, patients will have the right to change their mind and go spontaneously to the GPC. Another difference is the communication to the patient: during intervention weekends, we will inform them about the intervention using leaflets and broadcasting in the waiting room of the ED. During control weekends, we will only inform about MTS-triage in general but no about the GPC. We will always mention the iCAREdata opting-out procedure.

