#### Recruitment strategy and expected dropout

Unlike most trials, we do not foresee any recruitment problems. In 2016, 8000 patients presented themselves during the weekend at the ED.

For each patient the study period is the time between presentation at the ED and discharge at either the ED or the GPC. This is a time span of only a few hours so the dropout rate will be negligible. Only when a patient leaves the site before consultation at the ED or GPC he or she is a dropout. This number of patients leaving the ED without being seen after triage (i.e. dropouts) is one of the safety indicators we will study. The number of these patients is currently less than five per weekend. We are able to measure this number using the triage reports through iCAREdata. Patients who leave without being seen before the triage-consultation will not be analysed.

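### Question 8 gives two-week ED returns only by Table 2 cell, so as worded it cannot show whether the intervention changes returns; the randomised comparison should be added.

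*Combined protocol and SAP*

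**What the plan says.** Question 8 (Hypotheses and Research questions, medical aspect) reads: "What is the proportion of patients who return to the ED within two weeks for each of the categories described in table 2". The table it points to is captioned "Table 2: patient categories for the eMTS as a diagnostic instrument". It crosses the nurse's advice, the patient's destination and the physician's opinion after the consultation. Table 1 has a column for patients who leave unseen after triage (for example "Left without being seen type 1"); Table 2 does not.

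Questions 1, 5, 7, 9, 10 and 11 ask for an intervention effect or a difference between weekend types. Question 8 does not. Under Design of the clinical trial the protocol says: "To allow definitive conclusions for our questions we need a control group". It adds that in control weekends "all data registration and collection will be the same as during intervention weekends but we will not inform patients about their allocation advice". Methodology for the medical aspect gives one generic approach for questions 1 to 8, a non-linear mixed model. Weekend type is not among the explanatory variables it lists, although that list is left open-ended.

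Safety belongs to the medical aspect, which asks: "is this service capable of handling the medical problem in an efficient and qualitative way? Is it safe". Each patient's study period ends at discharge (Recruitment strategy and expected dropout), and costs stop at the out-of-hours consultation (Methodology for the financial aspects).

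**The concern.** Diversion to the GPC could do harm that appears only afterwards, for instance as an unplanned ED visit days later. In this document only question 8 would pick that up. A separate protocol will cover the process aspects, including reported incidents, but it is not among the documents supplied.

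The patients who end up in the diverted cells are selected. Only the two lowest urgency categories can be allocated to primary care, and the patient then has to accept. Their returns will probably be fewer than those of patients kept at the ED, whatever diversion does. Low figures in those cells could be taken as reassurance when they only reflect who was diverted. Randomising weekends removes that problem, but question 8 does not use it.

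**Working it through.** **Plan's own figure.** The documents give no expected return rate, ICC or precision for question 8, so there is nothing to reproduce. Assumed values are marked below.

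**1. When the cells are formed.** Weekends are randomised. Advice, destination and opinion all follow. Destination is what the intervention is meant to change, so the make-up of a cell differs by weekend type even if diversion has no effect on returns. The tables are built on compliance with advice, and control patients are not told theirs, so Table 2 most naturally describes intervention weekends only. On that reading question 8 contains no control patients.

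**2. What a contrast between cells would show (assumed values).** Let diverted patients have a 4% return risk if kept at the ED and a true increase of 2 points if diverted. Let patients advised to stay, who do stay, have a risk *g* points higher than 4%. The apparent difference is 2 - *g*:

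- *g* = 1 gives +1 point.
- *g* = 4 gives -2 points.

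A simulation with assumed parameters agrees. Mean return was 6%, rising with severity; sicker patients were less often diverted; about 31% had a GPC advice; 19% were seen at the GPC in intervention weekends and 1% in control weekends.

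| | No effect | True +2 points per diverted patient |
|---|---|---|
| Correct decision 1, intervention weekends | 2.3% | 4.3% |
| Correct decision 4, intervention weekends | 8.0% | 7.9% |
| All patients, control weekends | 6.0% | 6.0% |
| All patients, intervention weekends | 6.0% | 6.4% |

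With real harm, the diverted cell still looks far better than the ED cell. The all-patient comparison moves by the expected 2 x (0.191 - 0.010) = 0.36 points.

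**3. Patients without a cell.** On those who leave after triage without being seen, the protocol says: "The number of these patients is currently less than five per weekend". Included patients per weekend are 8000/52 - 15 = 138.8 (2016 volume; estimated exclusions), so five would be 5/138.8 = 3.6%. That is a ceiling.

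**4. Precision of the randomised comparison.** Control weekends: one per month gives 12, one per four intervention weekends gives 52/5 = 10.4, and one in four would give 13; I use *c* = 10 to 13 of 52. Assumed: return rate *p* 3-10%, ICC 0-0.01, and 20-30% of patients with a GPC advice. With *m* patients per weekend:

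- DE = 1 + (*m* - 1) x ICC
- half-width = 1.96 x sqrt( *p*(1 - *p*) x DE x [1/(*cm*) + 1/((52 - *c*)*m*)] )

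| Population | Inputs | Control / intervention patients | DE | Half-width (points) |
|---|---|---|---|---|
| All included | *m* = 138.8, *c* = 13, *p* = 3%, ICC 0 | 1805 / 5415 | 1.00 | 0.9 |
| All included | *m* = 138.8, *c* = 10, *p* = 10%, ICC 0.01 | 1388 / 5832 | 2.38 | 2.7 |
| GPC-advised | *m* = 41.7, *c* = 13, *p* = 3%, ICC 0 | 542 / 1625 | 1.00 | 1.7 |
| GPC-advised | *m* = 27.8, *c* = 10, *p* = 10%, ICC 0.01 | 278 / 1166 | 1.27 | 4.4 |

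**5. Dilution.** If 50-75% of GPC-advised patients go (assumed), 2 points per diverted patient becomes 0.2 x 0.5 x 2 = 0.2 to 0.3 x 0.75 x 2 = 0.45 points over all patients. That is below every half-width in the table.

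**The case against.** The strongest reply is that question 8 is descriptive. It sits with the questions on triage as a diagnostic instrument and asks what happens after right and wrong decisions; questions 2, 3 and 4 carry no weekend contrast either. The protocol never promises that question 8 will show an effect of diversion, and its general statement about the control group, with the open-ended variable list, may allow for one. This stands as a defence of the breakdown, which should stay. It does not supply the comparison: none is named for returns, and no other outcome here covers the period after discharge.

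A second reply is that the added comparison would usually miss the modest harm used above. That is correct, and it limits what the result can claim. A wide interval around a fair comparison still says which increases are excluded.

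A reader might infer three stronger things that the documents do not support:

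- **That returns in *false positive 1* are about 100% by definition.** The text does say of these patients: "This category is the same as the proportion of study patients allocated to the GP but referred back to the ED". But Methodology for the medical aspect counts referral to any ED, which need not be a new registration at this one, and any artefact stays within that cell. What remains is that question 8 does not say whether the referral counts as a return.
- **That refusers and uninformed control patients are pooled in the same cells.** This requires applying compliance-based categories to patients never told their advice, which is the less likely reading.
- **That comparing GPC-advised patients between weekend types is free of selection.** The advice follows randomisation and rests on answers entered by unblinded nurses, and control patients may go to the GPC on their own.

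**Conclusion.** The point holds as a gap in what question 8 asks. The cell proportions describe different kinds of patient, and contrasts between them cannot separate case mix from an effect of diversion. Under the assumed values a true increase of 2 points could appear as anything from +1 to -2. Patients who leave unseen after triage fall outside the question; they are few, but the protocol treats them as a safety indicator.

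A reader might go further and conclude that the trial ignores safety or cannot study returns. Neither follows. Leaving unseen is addressed as an intervention effect in question 5, incidents go to the process protocol, and registration is the same in both weekend types, so the data are planned. The primary result is unaffected. The return rate, ICC, advice share and uptake are my assumptions; the documents give none.

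**What to change.** Keep the Table 2 breakdown, labelled descriptive. Add to question 8 the difference between intervention and control weekends in the proportion of all triaged patients with a new ED registration within two weeks of the index visit, specified as follows:

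- Count each patient by the weekend type of the index visit.
- Include patients who left without being seen after triage.
- Do not count the direct GPC-to-ED referral of the index episode as a return; question 2 already covers these referrals. State beforehand how such a referral is recognised in the linked reports.
- Use the planned mixed logistic model with weekend as cluster, and report the difference in proportions with its 95% CI.
- As a supporting analysis, give the same difference in patients with a system-generated eMTS GPC advice, noting that unblinded nurses enter the answers after randomisation.

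The cost is a reworded question, a rule for same-episode referrals and further runs of a planned model by the data manager; question 8 already needs the return data. The downsides should be stated with the result: only a sizeable rise can be ruled out, a null result does not show safety, and returns to other EDs or at times not held in iCAREdata are missed.
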